### *Statistical Analysis Plan*

To identify reductions in alcohol use and negative alcohol-related consequences among high school seniors over the duration of the study, we will evaluate each outcome using analysis of variance in a linear or generalized linear mixed model framework, with random effects of repeated observations on students, students nested in classes, periods or teachers, and within school. We will address the appropriateness of the model for non-normal outcomes and apply the appropriate distribution as necessary, and we will assess models for the necessity of all random effects using  $AIC_C$ . The fixed effects will include treatment (intervention, control), time (baseline, 6-weeks, and 6-months), and their interaction.

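### Read as random intercepts, the planned model tests a classroom-randomised treatment-by-time effect against within-student error, and no class-by-time term is listed

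*Combined protocol and SAP*

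**What the plan says.** The Statistical Analysis Plan evaluates each outcome by "analysis of variance in a linear or generalized linear mixed model framework". Its random part is "random effects of repeated observations on students", then "students nested in classes, periods or teachers, and within school". The fixed part is treatment, "time (baseline, 6-weeks, and 6-months), and their interaction". For non-normal outcomes the analysts will "apply the appropriate distribution as necessary". On selection, "we will assess models for the necessity of all random effects using" AICc.

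Sections E and F state that classrooms within the two schools are randomised. Section E's hypothesis is a reduction relative to control, which in this model is the treatment-by-time interaction.

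The plan does not say whether the random effects are intercepts or also include slopes. It lists no class-by-time effect and names no within-student covariance, robust standard error or degrees-of-freedom method. No number of classes is given.

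**The concern.** In a classroom-randomised trial with repeated measures, the error relevant to the interaction is how much classes differ from one another in their change. A class random intercept describes only how classes differ in level, and level drops out of a change. If classes drift apart for reasons unrelated to treatment, such as a teacher, a friendship group or an event, a model with intercepts alone attributes that drift to treatment and reports too small a standard error. The trial's main claim would then carry more false-positive risk than its nominal level.

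The unstated within-student covariance is a lesser worry. Visits at baseline, 6 weeks and 6 months are about 6, 20 and 26 weeks apart if both follow-ups are counted from baseline. A student intercept with one residual variance gives all three pairs the same correlation. The 6-month contrast matters because Section E presents longer follow-up as what the study adds.

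**Working it through.** **The plan's own figure.** Section F expects 45% of 1000 students: 1000 × 0.45 = 450, which reproduces. Its statement that this gives adequate power cannot be checked, because no effect size, SD, intraclass correlation or number of classes is given. Every variance, correlation and class count below is therefore an assumption.

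**Class-by-time part (linear model, complete data).** Write a student's outcome as arm-by-visit mean + school + class + student + class-by-time (variance τ²) + residual (variance σ²). In any change from baseline, the school, class and student intercepts subtract out. With m classes of k students, n = mk, and equal arms:

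- True variance of the difference in change between arms: (8/n)(σ² + kτ²).
- Variance reported by the intercept-only model: (8/n)D, where D = σ² + kτ²(m − 2)/(n − 2).
- Ratio R = (σ² + kτ²)/D. For the 2-df test at 5% (critical value 5.991), large-sample error = exp(−5.991/(2R)) = exp(−2.996/R).

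Inputs: total variance 1 and equal correlation 0.6 between visits, so σ² + τ² = 0.40; n = 440, close to the expected 450.

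| Classes × size | τ² | σ² + kτ² | D | R | Error, formula | Error, simulated |
|---|---|---|---|---|---|---|
| 40 × 11 | 0 | 0.40 | 0.400 | 1.00 | 5.0% | 5.3% |
| 40 × 11 | 0.01 | 0.39 + 0.11 = 0.50 | 0.39 + 0.11 × 38/438 = 0.400 | 1.25 | 9.1% | 8.8% |
| 40 × 11 | 0.02 | 0.38 + 0.22 = 0.60 | 0.38 + 0.22 × 38/438 = 0.399 | 1.50 | 13.6% | 14.6% |
| 20 × 22 | 0 | 0.40 | 0.400 | 1.00 | 5.0% | 5.1% |
| 20 × 22 | 0.01 | 0.39 + 0.22 = 0.61 | 0.39 + 0.22 × 18/438 = 0.399 | 1.53 | 14.1% | 15.1% |
| 20 × 22 | 0.02 | 0.38 + 0.44 = 0.82 | 0.38 + 0.44 × 18/438 = 0.398 | 2.06 | 23.4% | 23.7% |

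Formula and simulation agree to about one percentage point. A class-level test of the 6-month change held about 5% throughout. These settings have truly equal correlations, so this part does not depend on correlation decay.

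**Within-student part (225 per arm, SD 1, class effects ignored).** A student intercept with one residual variance gives both change contrasts the same SE, √(4(1 − r̄)/225), where r̄ is the mean of the three correlations. The true SE is √(4(1 − r)/225), where r is the correlation between baseline and that visit. Error = 2(1 − Φ(1.96 × model SE/true SE)). Correlations are listed as baseline–6 weeks / 6 weeks–6 months / baseline–6 months.

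- 0.70/0.60/0.50: model SE √(1.6/225) = 0.0843. True SE is √(1.2/225) = 0.0730 at 6 weeks (error 2.4%) and √(2.0/225) = 0.0943 at 6 months (error 8.0%).
- 0.65/0.60/0.55: model SE 0.0843, true 0.0789 and 0.0894; errors 3.6% and 6.5%.
- 0.65/0.60/0.45: 6-month error 8.2% by formula, and 8.4–8.7% in simulations that add class clustering.
- Steeper, continuous-time autoregressive decay with a 6-week correlation of 0.7–0.9: 6-month error 8.9–10.3%.
- Equal correlations of 0.6: no error at either visit.
- 0.60/0.40/0.55: the 6-month SE is 4% too large.
- 0.55/0.70/0.50: the 6-week SE is 4% too small.
- 0.65/0.60/0.55 with SDs falling 1.2, 0.9, 0.8: the 6-week SE is 2% too small.

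The 2-df interaction test has error of only 5.1–5.3% under the first three patterns. In a Poisson model with a log-scale student intercept (variance 1) and visit means 0.5, 1 and 2, observed-scale correlations are 0.54/0.70/0.60, so they are not equal.

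**The case against.** The strongest objection is that the plan never states an intercept-only model. Its wording does not exclude random slopes or a structured residual covariance, and it promises to examine the random effects. That stands as a limit on certainty. It does not remove the gap, because AICc is applied to whether random effects are needed, which can drop a term, and no class-by-time term is listed for it to keep.

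A second objection is that the natural test is the 2-df interaction, which correlation decay barely disturbs. That is correct and disposes of most of the within-student part. It does not answer the class-by-time part, since the inflation in the table is for that same 2-df test.

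Two stronger readings are tempting. A reader might infer that the student effect forces equal correlation, so that the 6-month standard error must be too small and the 6-week one too large. The documents do not support this: they give no correlations or variances, the direction changes under plausible alternatives, and equal correlation does not carry over to the observed scale in the generalized models the plan allows. A reader might also infer a test against a normal reference with very few clusters. The plan states neither a reference distribution nor a class count.

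**Conclusion.** The concern holds as a conditional specification gap. On the most natural reading of the plan, nested intercepts in a linear model, the effect of a classroom-randomised intervention is tested against within-student error. The 2-df test then rejects too often whenever classes differ in their change: about 9–15% with 40 classes of 11 and 15–24% with 20 classes of 22, if class-by-time variance is 1–2% of the total. With none, the error is about 5%. These sizes assume complete data, equal arms and a correlation of 0.6.

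The unspecified within-student covariance is secondary. It matters for visit-specific contrasts and intervals if correlation decays and variances are similar (about 6.5–8.5% at 6 months under moderate decay, conservative at 6 weeks). It matters little for the joint test.

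**What to change.** In the Statistical Analysis Plan:

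- Add a class-by-time random effect for the randomised classroom, kept regardless of AICc, and name the classroom rather than leaving class, period or teacher open.
- For linear models, replace the student effect with an unstructured 3×3 within-student covariance. For count models, use visit-specific student effects if they can be fitted, otherwise cluster-robust standard errors by class with a small-sample correction.
- For linear models, use Kenward-Roger or Satterthwaite degrees of freedom.
- State the planned number of classrooms.

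The cost is wording and a few parameters: the unstructured covariance has six (three variances, three covariances) against two for an intercept plus residual, and the class-by-time effect adds at least one variance. Count models with several correlated effects may fail to converge, hence the stated fallback. Intervals become somewhat wider. In the tabulated settings with class-by-time variance, standard errors rise by a factor of √1.25 = 1.12 to √2.06 = 1.44, which is the uncertainty the intercept-only model omits.

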The proposed study extends the literature by examining the eCHECKUP TO GO with high school seniors over a longer follow-up period, as well as examining mediators and moderators of intervention effects. All 12th grade students at the two participating school sites will be given the opportunity to participate in the study. All participants will complete an assessment packet containing questionnaires including demographic

information, the quantity and frequency of their drinking, beliefs about both the quantity and frequency of their peers' drinking, alcohol beliefs and expectancies, problems associated with drinking, personality characteristics, and future goals (see attachment 1). Classrooms within the high school schools will be randomly assigned to the following groups: eCHECKUP TO GO and control group.

What is your research question? State your hypothesis.

**The project is designed to evaluate the following hypothesis:** Participants in the eCHECKUP TO GO intervention condition will report a reduction in their quantity of alcohol consumption and alcohol-related consequences relative to those in the control group. We are also interested in mechanisms of change (e.g. changes in estimates of peer drinking and/or drinking expectancies) and if this program is more effective for some students than others (e.g. gender, baseline drinking status, social-emotional maturity, college-bound status).

What will you do with the results of your study (e.g. contributing to generalizable knowledge, publishing, sharing at conference, etc.)? If this project is only for internal evaluation or to complete a class assignment, IRB may not be required. Please contact the ORC for additional information.

**Results of this study will be presented at conferences via oral or poster presentations and through publication in peer-reviewed journals. In addition a project summary report will be sent to the participating schools and/or school district.**

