**We anticipate the student participants will be healthy.**

2. Will your research involve vulnerable populations, such as children or adolescents under the age of 18, pregnant women, prisoners or cognitively, economically, or educationally impaired participants?

NO  YES (indicate population): \_\_\_\_\_

If yes, describe additional safeguards planned to protect the rights and welfare of this population(s):

Student participants recruited to this research study will be approximately 1000 high school seniors (ages 16-18) from Capital High School and Boise High School in the Boise School District. Classrooms within the schools will be randomized to intervention or assessment-only control conditions. Participants will be recruited from classes. A letter will be sent by the schools to parents and their students prior to the study explaining the research. Parents will be asked to return consent forms using a self-addressed stamped postcard. Students will be invited to participate in the research study during class. Those students who decline participation will participate in an alternate academic activity under the supervision of the teacher. Consent procedures will be the same for minors and 18 year old students as the Boise School District requires parental consent for 18 year old students.

The surveys will ask student participants about their own alcohol use/non-use and any negative consequences, attitudes and beliefs about alcohol use, reasons for using alcohol use, norms for alcohol use, personality characteristics, future plans, and demographic information. Similar procedures have been used in previous research with 9th grade students and high school seniors without adverse incident. Psychological risks posed by the research are primarily related to the content of the assessment measures. Items include thoughts and feelings that may be private and personal behavior such as alcohol use. These questions may make participants uncomfortable, or be perceived as an intrusion on their privacy. Although it is important to consider these potential risks, and it is important to point out the potential for these risks, we have not observed any indications of these risks materializing in all of our previous research using procedures similar to those we will use in the proposed study.

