All data and other information in this study will be maintained confidentially, but data will not be anonymous due to the longitudinal nature of participation. In order to protect against risks posed by the potential loss of confidentiality, we will take the following steps: 1) participants will be assured that they are free to refrain from answering any questions they do not wish to answer; 2) all data will be identified only by a unique personal identifier (PIN), which will be randomly generated for study purposes; 3) a master list of names and code numbers will be stored in locked file cabinets under the supervision of the PI and will be available only to research staff on this project. Data will be retained on computers with restricted and password protected access, without links to the master code list. All data based on this research will be reported in aggregate form.

3. Will you be recruiting students from a class that you teach? (See IRB [guidelines](#) for using your own students.)
 

NO  YES

If yes, explain why this population is necessary to the study, and how you will ensure participants do not feel coerced to participate. Coercion is a significant concern.
4. Will you be recruiting employees who report to you?
 

NO  YES

If yes, explain why this population is necessary to the study, and how you will ensure participants do not feel coerced to participate. Coercion is a significant concern.
5. Indicate any exclusion criteria for participants.  
**There are no exclusion criteria for recruitment other than not meeting inclusion criteria other than not being a senior at one of the two school sites.**
6. How many participants do you anticipate are needed for this research?  
**We anticipate a 45% response rate (students with parental active consent, student assent, and who are present the day of data collection) - this will yield 450 student participants in this study which will provide a large enough sample to adequately power this study.**

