**Applications missing this section will not be accepted.**

All student participants will be asked to complete an online survey during class time. This will take no longer than 20 minutes. Participants in the classrooms randomly assigned to the intervention group will be asked to complete an online intervention program which will occur during class time. The program involves a comprehensive assessment of the participant's drinking and drinking-related behaviors, followed by systematic personalized feedback to the participant about their alcohol use feedback in relation to their peer group. The program will take about 30 minutes to complete. Participants will then be asked to complete a brief exit survey regarding the intervention. Participants will be asked to complete the survey at 6 weeks and 6 months in the computer lab at their school. This survey will be completed online during class periods and will take no longer than 20 minutes to complete. Participants will also complete a very brief survey to assess help seeking. This will occur at the 6 week and 6 month follow-up assessments.

5. Where will the data collection and data analysis procedures take place? (i.e., explain where you are distributing surveys, conducting interviews, etc.)

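### AICc screening of all random effects has no exemption for the randomised classroom, so comparisons of levels between arms can be tested on student-level error

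*Combined protocol and SAP*

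**What the plan says.** The unit of randomisation is the classroom, and the protocol says so three times:

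- Section E (Purpose): "Classrooms within the high school schools will be randomly assigned to the following groups: eCHECKUP TO GO and control group".
- Section F, item 2: "Classrooms within the schools will be randomized to intervention or assessment-only control conditions".
- Section H, item 4: "Participants in the classrooms randomly assigned to the intervention group will be asked to complete an online intervention program".

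The Statistical Analysis Plan fits a linear or generalized linear mixed model. Its random effects cover repeated measures within student and "students nested in classes, periods or teachers, and within school". It then states: "we will assess models for the necessity of all random effects using" AICc. No sentence there or elsewhere says that classroom is retained regardless.

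On the fixed side: "The fixed effects will include treatment (intervention, control), time (baseline, 6-weeks, and 6-months), and their interaction". None of these is named as the efficacy test. The hypothesis in Section E is that intervention students "will report a reduction in their quantity of alcohol consumption and alcohol-related consequences relative to those in the control group".

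**The concern.** When classrooms are randomised, between-class variance belongs to the error of any comparison of arm levels. That follows from the design and should not depend on whether this sample detects the variance. With few classes and a small ICC, the likelihood gain from a class term is often too small to pay the AICc penalty, even though the variance is there. The term is then dropped, and standard errors for the treatment main effect and for arm differences at 6 weeks or 6 months are computed as if students had been randomised one by one.

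The listing of groupings joined by *or* adds to this. It does not guarantee that the randomised grouping is in the model to begin with.

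What is at stake is an excess of false positives for level comparisons. Treatment-by-time is a different matter, as shown below.

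**Working it through.** **Inputs from the documents.** Section F gives 1000 seniors and a 45% response rate: 1000 × 0.45 = 450, which agrees with "this will yield 450 student participants in this study". There are three time points (Statistical Analysis Plan).

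**Assumed, because the documents do not give them.** Number and size of classes, ICC, two-sided 5% level, equal allocation, no dropout and normal outcomes. No true effect is present in any simulation.

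**Step 1: the AICc hurdle.** The penalty is 2k + 2k(k+1)/(n−k−1). With n = 3 × 450 = 1350:

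- k = 9 (class in): 18 + 180/1340 = 18.13
- k = 8 (class out): 16 + 144/1341 = 16.11

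Class is kept only if it raises twice the log-likelihood by more than about 2.03.

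**Step 2: what happens if it is dropped.** The variance of an arm difference is understated by roughly the design effect, 1 + (m−1) × ICC. For 18 classes of 25 at ICC 0.02 this is 1 + 24 × 0.02 = 1.48. The test at 1.96 really operates at 1.96/√1.48 = 1.61, a two-sided error of about 10.7%. Simulation gives 10.8% among trials where class is dropped.

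**Step 3: the AICc rule over a range of class numbers.** There were 200,000 null trials per row, with ML selection. The ICC is that of the student's mean over time. A dropped class gives a test on N−2 df and a kept class gives one on K−2 df.

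| Classes × size | ICC | Design effect | Class dropped | Error if dropped | Error under AICc rule | Error, class always kept |
|---|---|---|---|---|---|---|
| 10 × 45 | 0.01 | 1.44 | 86.0% | 10.3% | 8.9% | 5.0% |
| 10 × 45 | 0.02 | 1.88 | 68.5% | 15.5% | 10.8% | 5.0% |
| 10 × 45 | 0.05 | 3.20 | 27.8% | 28.4% | 9.4% | 5.1% |
| 10 × 45 | 0.10 | 5.40 | 6.5% | 41.7% | 6.2% | 5.0% |
| 18 × 25 | 0.02 | 1.48 | 71.0% | 10.8% | 8.0% | 4.9% |
| 18 × 25 | 0.05 | 2.20 | 27.2% | 19.1% | 7.4% | 5.0% |
| 18 × 25 | 0.10 | 3.40 | 3.8% | 30.5% | 5.5% | 5.0% |
| 30 × 15 | 0.02 | 1.28 | 75.3% | 8.4% | 6.8% | 5.0% |
| 30 × 15 | 0.05 | 1.70 | 32.3% | 13.4% | 6.6% | 5.0% |
| 46 × 10 | 0.02 | 1.18 | 78.3% | 7.1% | 6.1% | 5.0% |
| 46 × 10 | 0.05 | 1.45 | 38.9% | 10.3% | 6.2% | 4.9% |

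The overall rate is well below the rate among dropped trials because kept trials rarely reject. At 18 × 25 and ICC 0.02, dropped trials contribute 0.710 × 10.8 = 7.7 points of the 8.0. Selecting by REML instead of ML lowers the largest overall figure to 9.1%.

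**Step 4: the plan's three-time-point model.** Student and class intercepts, treatment, time and their interaction; 40 classes of 11 or 20 of 22 (440 students); within-student correlation 0.6; 400,000 trials per cell; AICc on 1,320 observations.

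| Test | AICc rule, ICC 0.02–0.05 | Class always kept |
|---|---|---|
| Treatment main effect | 5.9–8.0% | 4.6–5.0% |
| 6-month arm difference | 5.7–7.0% | 4.8–5.0% |
| Treatment-by-time | 4.9–5.1% | not affected |

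Class is dropped in 15–69% of these trials. At ICC 0.10 it is dropped in about 1%, and error is 5.0–5.2%.

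**Step 5: why treatment-by-time escapes.** A class intercept is the same at every time point, so it subtracts out of each student's change. In a separate check (18 × 25, 4,000 trials) with no class term at all and class variance 0.05 or 0.10, treatment-by-time rejected in 4.6% and 4.8% of trials. The level comparison rejected in 23% and 35%.

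**The case against.** The strongest reply is that the hypothesis concerns a reduction relative to control, which is treatment-by-time, and that test is not inflated. This stands. However, the plan does not confine inference to the interaction. It fits a treatment main effect too, and nothing stops a 6-month arm difference from being reported as an efficacy result. It is fair to add that the main effect averages in the baseline level and so is an unlikely efficacy test. That makes the time-point difference the more realistic exposure, at 5.7–7.0%.

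Second, the excess is only 1–3 points in the three-time-point model and rests on inputs absent from the documents. This also stands. Varying the within-student correlation from 0.3 to 0.8 moves the low end to about 5.2–5.4%. In the other direction, 10 classes of 45 give up to 10.8% in Step 3, so 20–40 classes is not the worst case.

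Third, the plan speaks of assessing necessity and sets no cut-off. Removing class when AICc is not lower with it is the ordinary reading, but it is an inference. A retained teacher or period term might also absorb some class variance, which was not modelled.

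Fourth, the interaction has a different weakness: no class-by-time term is listed. In the Step 5 check, an added class-by-time variance of 0.02 took its error to 23%. That is a separate gap, and a class intercept does not address it.

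**Conclusion.** The concern holds, for comparisons of levels only. As written, the rule can remove the randomised unit from the model and test the treatment main effect or a time-point arm difference on student-level error.

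Under the assumptions of Step 4 the error is about 6–8% instead of 5%. It is higher with fewer classes and close to nominal at ICC 0.10. A team that finds AICc has dropped classroom faces the rate conditional on that: about 7–18% with one value per student, 20–40 classes and ICC 0.02–0.05.

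No inflation is claimed for treatment-by-time from a class intercept, and no figure is offered for non-normal outcomes, for the school effect or for classes that differ in change. The point should be fixed, but it does not undermine the main hypothesis test.

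**What to change.** Add to the Statistical Analysis Plan:

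> The randomised classroom is included as a random effect in every model, whatever its AICc, and treatment comparisons of levels are tested on class-level degrees of freedom. AICc is used only for further terms such as period or teacher, added to classroom and never in its place.

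Say also that the list of groupings always includes classroom. If a class-by-time term is fitted for the treatment-by-time test, exempt it from AICc screening too. For the 6-month difference, name the degrees of freedom: number of classes minus 2 is slightly conservative (4.1–4.7%), while Satterthwaite gives 4.7–5.1%.

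The cost is some precision in level comparisons. If classes truly do not differ and the class variance is held at zero or above, intervals are about 7% wider with 40 classes and 13% wider with 20, and the test is conservative (3.7% and 2.9%). Most of that comes from the zero constraint: with an unconstrained class variance the widening is 2.4% and 5.5%, and error is 5.0–5.1%. At ICC 0.02–0.05, intervals are 4–12% wider than under the AICc rule. The class intercept costs treatment-by-time nothing; a class-by-time term would cost it some precision. No change to design or data collection is needed.
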